10.1.9 Study and site closure

The Sponsor or designee reserves the right to close the study site or terminate the study at any time for any reason at the sole discretion of the Sponsor. Study sites will be closed upon study completion. A study site is considered closed when all required documents and study supplies have been collected and a study-site closure visit has been performed.

The Investigator may initiate study-site closure at any time, provided there is reasonable cause and sufficient notice is given in advance of the intended termination.

Reasons for study termination by the Sponsor, as well as reasons for the early closure of a study site by the Sponsor or Investigator may include but are not limited to:

- For study termination:
 - Information on the product leads to doubt as to the benefit/risk ratio
 - Discontinuation of further study intervention development
- For site termination:
 - Failure of the Investigator to comply with the protocol, the requirements of the IRB/IEC or local health authorities, the Sponsor's procedures, or GCP guidelines
 - Inadequate or no recruitment (evaluated after a reasonable amount of time) of participants by the Investigator
 - Total number of participants included earlier than expected

10.1.10 Publication policy

- The results of this study may be published or presented at scientific meetings. If this is foreseen, the Investigator agrees to submit all manuscripts or abstracts to the Sponsor before submission. This allows the Sponsor to protect proprietary information and to provide comments.
- The Sponsor will comply with the requirements for publication of study results. In accordance with standard editorial and ethical practice, the Sponsor will generally support publication of multicenter studies only in their entirety and not as individual site data. In this case, a coordinating Investigator will be designated by mutual agreement.
- Authorship will be determined by mutual agreement and in line with International Committee of Medical Journal Editors authorship requirements.

10.2 APPENDIX 2: CLINICAL LABORATORY TESTS

The tests detailed in [Table 11](#) will be performed by the local laboratory.

- The results must be entered into the eCRF.
- Protocol-specific requirements for inclusion or exclusion of participants are detailed in [Section 5](#) of the protocol.
- Additional tests may be performed at any time during the study as determined necessary by the Investigator or required by the local regulations.
- For women of childbearing potential (WOCBP), a serum pregnancy test will be performed at screening. For all other planned time points (see [Section 1.3](#)), a serum or urine human chorionic gonadotropin (hCG) pregnancy test will be performed. Pregnancy test can be performed at home for participants during the FUP or if date of test does not match with FUP visit and the site must record this in the source document. Test should be performed at Screening (ie, ≤ 7 days prior to first IMP), C2D1, C3D1, at the end of isatuximab treatment (ie, Week 1 of site visit FUP or E/D visit [± 7 days]), and 5 months (± 7 days) after the last dose of IMP.

Table 11 - Protocol-required safety laboratory assessments

Laboratory assessments	Parameters
Hematology	Platelet count RBC count Hemoglobin Hematocrit WBC count with differential: Neutrophils (absolute neutrophil count) Lymphocytes Monocytes Eosinophils Basophils
Clinical chemistry	Urea or BUN Uric acid Creatinine eGFR (MDRD) Glucose fasting Hemoglobin A1c (screening, site visit FUP Week 9, E/D visit; and as clinically indicated) Potassium Chloride Sodium Magnesium Phosphate Calcium Bicarbonate (screening, site visit FUP Week 9, E/D visit; and as clinically indicated)

Laboratory assessments	Parameters
	AST/SGOT
	ALT/SGPT
	Alkaline phosphatase
	Total and direct bilirubin
	LDH
	Total protein
	Albumin
	PTH assessment (screening, site visit FUP Week 9, E/D visit; and as clinically indicated)
Other tests	
Coagulation: prothrombin time or INR, and activated PTTBlood typing interference test (see Section 1.3, footnote ⁱ)Serology^a: HBV (HBsAg, anti-HBc [total and IgM], anti-HBs), HCV (anti-HCV), HIV (HIV antibody), CMV (IgG and IgM), EBV (early antigen, VCA-IgG, VCA-IgM, nuclear antigen antibody)Viral load^a: HBV DNA, HCV RNA, EBV DNA, CMV DNA
	The results of each test must be entered into the eCRF

Abbreviations: anti-HBc = antibody to hepatitis B core antigen; anti-HBs = antibody to hepatitis B surface antigen; ALT = alanine aminotransferase, AST = aspartate aminotransferase, BUN = blood urea nitrogen, CMV = cytomegalovirus, EBV = Epstein-Barr virus, eCRF = electronic case report form, E/D = early discontinuation, eGFR = estimated glomerular filtration rate, DNA = deoxyribonucleic acid, FUP = follow-up period, HBV = hepatitis B virus, HBsAg = hepatitis B surface antigen, HCV = hepatitis C virus, HIV = human immunodeficiency virus, IgG= immunoglobulin G, IgM = immunoglobulin M, INR = international normalized ratio, LDH = lactic acid dehydrogenase, MDRD = Modification of Diet in Renal Disease, PTH = parathyroid hormone, PTT = partial thromboplastin time, RBC = red blood cell, RNA = ribonucleic acid, SGOT = serum glutamic-oxaloacetic transaminase, SGPT = serum glutamic-pyruvic transaminase, VCA = viral capsid antigen, WBC = white blood cell.

NOTES: Blood chemistry, hematology: assessments are not required to be repeated prior to Cycle 1 Day 1 if the screening laboratory assessments were performed within 7 days prior to first the IMP administration and met entry criteria. The window for blood chemistry and hematology is within 1 working day prior to IMP administration.

a Study sites should determine which serology and viral load tests are required to confirm participant's eligibility and to enable appropriate viral reactivation monitoring for HBV, HCV, HIV, EBV, and CMV as per protocol. The tests listed serve as a guidance and may not require all tests to be performed if selective results are conclusive on participant's viral infection status and sufficiently support safety monitoring.

Investigators must document their review of each laboratory safety report.

10.3 APPENDIX 3: ADVERSE EVENTS: DEFINITIONS AND PROCEDURES FOR RECORDING, EVALUATING, FOLLOW-UP, AND REPORTING

DEFINITION OF AE

AE definition

- An AE is any untoward medical occurrence in a patient or clinical study participant, temporally associated with the use of study intervention, whether or not considered related to the study intervention.
- NOTE: An AE can therefore be any unfavorable and unintended sign (including an abnormal laboratory finding), symptom, or disease (new or exacerbated) temporally associated with the use of study intervention.

Events meeting the AE definition

- Any abnormal laboratory test results (hematology, clinical chemistry, or urinalysis) or other safety assessments (eg, ECG, radiological scans, vital signs measurements), including those that worsen from baseline, considered clinically significant in the medical and scientific judgment of the Investigator (ie, not related to progression of underlying disease), eg:
 - Leading to IMP discontinuation or modification of dosing, and/or
 - Fulfilling a seriousness criterion, and/or
 - Defined as an AESI
- Exacerbation of a chronic or intermittent pre-existing condition including either an increase in frequency and/or intensity of the condition.
- New conditions detected or diagnosed after study intervention administration even though it may have been present before the start of the study.
- Signs, symptoms, or the clinical sequelae of a suspected drug-drug interaction.
- Signs, symptoms, or the clinical sequelae of a suspected overdose of either study intervention or a concomitant medication.

Events NOT meeting the AE definition

- Any clinically significant abnormal laboratory findings or other abnormal safety assessments which are associated with the underlying disease, unless judged by the Investigator to be more severe than expected for the participant's condition.
- The disease/disorder being studied or expected progression, signs, or symptoms of the disease/disorder being studied, unless more severe than expected for the participant's condition.
- Medical or surgical procedure (eg, endoscopy, appendectomy): the condition that leads to the procedure is the AE.
- Situations in which an untoward medical occurrence did not occur (social and/or convenience admission to a hospital).
- Anticipated day-to-day fluctuations of pre-existing disease(s) or condition(s) present or detected at the start of the study that do not worsen.

DEFINITION OF SAE

If an event is not an AE per definition above, then it cannot be an SAE even if serious conditions are met (eg, hospitalization for signs/symptoms of the disease under study, death due to progression of disease).

A SAE is defined as any untoward medical occurrence that, at any dose:

- a) Results in death**
- c) Is life-threatening**

The term “life-threatening” in the definition of “serious” refers to an event in which the participant was at risk of death at the time of the event. It does not refer to an event, which hypothetically might have caused death, if it were more severe.

d) Requires inpatient hospitalization or prolongation of existing hospitalization

In general, hospitalization signifies that the participant has been detained (usually involving at least an overnight stay) at the hospital or emergency ward for observation and/or treatment that would not have been appropriate in the physician’s office or outpatient setting. Complications that occur during hospitalization are AEs. If a complication prolongs hospitalization or fulfills any other serious criteria, the event is serious. When in doubt as to whether “hospitalization” occurred or was necessary, the AE should be considered serious.

Hospitalization for elective treatment of a pre-existing condition that did not worsen from baseline is not considered an AE.

e) Results in persistent disability/incapacity

- The term disability means a substantial disruption of a person’s ability to conduct normal life functions.
- This definition is not intended to include experiences of relatively minor medical significance such as uncomplicated headache, nausea, vomiting, diarrhea, influenza, and accidental trauma (eg, sprained ankle) which may interfere with or prevent everyday life functions but do not constitute a substantial disruption.

f) Is a congenital anomaly/birth defect

g) Other situations:

- Medical or scientific judgment should be exercised in deciding whether SAE reporting is appropriate in other situations such as important medical events that may not be immediately life-threatening or result in death or hospitalization but may jeopardize the participant or may require medical or surgical intervention to prevent one of the other outcomes listed in the above definition. These events should usually be considered serious.
- Examples of such events include invasive or malignant cancers, intensive treatment in an emergency room or at home for allergic bronchospasm, blood dyscrasias or convulsions that do not result in hospitalization, or development of drug dependency or drug abuse.

RECORDING AND FOLLOW-UP OF AE AND/OR SAE

AE and SAE recording

- When an AE/SAE occurs, it is the responsibility of the Investigator to review all documentation (eg, hospital progress notes, laboratory reports, and diagnostics reports) related to the event.
- The Investigator will then record all relevant AE/SAE information in the eCRF.

- It is **not** acceptable for the Investigator to send photocopies of the participant's medical records to Sponsor in lieu of completion of the AE/SAE eCRF page.
- There may be instances when copies of medical records for certain cases are requested by Sponsor. In this case, all participant identifiers, with the exception of the participant number, will be redacted on the copies of the medical records before submission to Sponsor.
- The Investigator will attempt to establish a diagnosis of the event based on signs, symptoms, and/or other clinical information. Whenever possible, the diagnosis (not the individual signs/symptoms) will be documented as the AE/SAE.

Assessment of intensity

The NCI-CTCAE version 5.0 will be used to assess the severity of AEs/SAEs

Assessment of causality

- The Investigator is obligated to assess the relationship between study intervention and each occurrence of each AE/SAE.
- A “reasonable possibility” of a relationship conveys that there are facts, evidence, and/or arguments to suggest a causal relationship, rather than a relationship cannot be ruled out.
- The Investigator will use clinical judgment to determine the relationship.
- Alternative causes, such as underlying disease(s), concomitant therapy, and other risk factors, as well as the temporal relationship of the event to study intervention administration will be considered and investigated.
- The Investigator will also consult the Investigator's Brochure and/or Product Information, for marketed products, in his/her assessment.
- For each AE/SAE, the Investigator **must** document in the medical notes that he/she has reviewed the AE/SAE and has provided an assessment of causality.
- There may be situations in which an SAE has occurred and the Investigator has minimal information to include in the initial report to Sponsor. However, **it is very important that the Investigator always make an assessment of causality for every event before the initial transmission of the SAE data to Sponsor**
- The Investigator may change his/her opinion of causality in light of follow-up information and send a SAE follow-up report with the updated causality assessment.
- The causality assessment is one of the criteria used when determining regulatory reporting requirements.

Follow-up of AEs and SAEs

- The Investigator is obligated to perform or arrange for the conduct of supplemental measurements and/or evaluations as medically indicated or as requested by Sponsor to elucidate the nature and/or causality of the AE or SAE as fully as possible. This may

include additional laboratory tests or investigations, histopathological examinations, or consultation with other health care professionals.

- New or updated information will be recorded in the originally completed CRF.
- The Investigator will submit any updated SAE data to the Sponsor within 24 hours of receipt of the information.

REPORTING OF SAES

SAE reporting to Sponsor via an electronic data collection tool

- The primary mechanism for reporting an SAE to Sponsor will be the electronic data collection tool.
- If the electronic system is unavailable, then the site will use the paper SAE data collection tool (see next section) in order to report the event within 24 hours.
- The site will enter the SAE data into the electronic system as soon as it becomes available.
- After the study is completed at a given site, the electronic data collection tool will be taken off-line to prevent the entry of new data or changes to existing data.
- If a site receives a report of a new SAE from a study participant or receives updated data on a previously reported SAE after the electronic data collection tool has been taken off-line, then the site can report this information on a paper SAE form (see next section) or to the Sponsor by telephone.
- Contacts for SAE reporting can be found in the Investigator Study File.

SAE reporting to Sponsor via paper CRF

- Facsimile transmission of the SAE paper CRF is the preferred method to transmit this information to the Sponsor if the electronic system is unavailable.
- In rare circumstances and in the absence of facsimile equipment, notification by telephone is acceptable with a copy of the SAE data collection tool sent by overnight mail or courier service.
- Initial notification via telephone does not replace the need for the Investigator to complete and sign the SAE CRF pages within the designated reporting time frames.
- Contacts for SAE reporting can be found in the Investigator Study File.

10.4 APPENDIX 4: CONTRACEPTIVE GUIDANCE AND COLLECTION OF PREGNANCY INFORMATION

DEFINITIONS:

Woman of childbearing potential (WOCBP)

A woman is considered fertile following menarche and until becoming postmenopausal unless permanently sterile (see below).

If fertility is unclear (eg, amenorrhea in adolescents or athletes) and a menstrual cycle cannot be confirmed before first dose of study intervention, additional evaluation should be considered.

Women in the following categories are not considered WOCBP

1. Premenarchal
2. Premenopausal female with 1 of the following:
 - Documented hysterectomy
 - Documented bilateral salpingectomy
 - Documented bilateral oophorectomy

For individuals with permanent infertility due to an alternate medical cause other than the above, (eg, mullerian agenesis, androgen insensitivity), Investigator discretion should be applied to determining study entry.

Note: Documentation can come from the site personnel's: review of the participant's medical records, medical examination, or medical history interview.

3. Postmenopausal female

- A postmenopausal state is defined as no menses for 12 months without an alternative medical cause.
- A high follicle stimulating hormone (FSH) level in the postmenopausal range may be used to confirm a postmenopausal state in women not using hormonal contraception or hormonal replacement therapy (HRT). However, in the absence of 12 months of amenorrhea, confirmation with more than one FSH measurement is required.
- Females on HRT and whose menopausal status is in doubt will be required to use one of the non-estrogen hormonal highly effective contraception methods if they wish to continue their HRT during the study. Otherwise, they must discontinue HRT to allow confirmation of postmenopausal status before study enrollment.

CONTRACEPTION GUIDANCE:

Females of childbearing potential or male participants with female partners of childbearing potential are required to use effective contraceptive methods starting 2 weeks before IMP administration, during treatment period, and until 5 months after last dose of isatuximab.

Male participants

- Male participants with heterosexual partners of reproductive potential (WOCBP) are eligible to participate if they agree to use the following during the protocol defined timeline:
 - Refrain from donating sperm

and

- At least 1 of the following conditions applies:

Are and agree to remain abstinent from penile-vaginal intercourse on a long-term and persistent basis, when this is their preferred and usual lifestyle,

or

Agree to use a male condom plus an additional contraceptive method with a failure rate of <1% per year (see table for female participants).

- Male participants with a pregnant or breastfeeding partner must agree to remain abstinent from penile-vaginal intercourse or use a male condom for the time defined in the protocol.

Female participants

Female participants of childbearing potential are eligible to participate if they agree to use a highly effective method of contraception consistently and correctly as described in [Table 12](#).

Table 12 - Highly effective contraceptive methods

Highly effective contraceptive methods that are user dependent^a

Failure rate of <1% per year when used consistently and correctly.

Combined (estrogen and progestogen containing) hormonal contraception associated with inhibition of ovulation^b

- Oral
- Intravaginal
- Transdermal

Progestogen only hormonal contraception associated with inhibition of ovulation

- Oral
- Injectable

Highly effective methods that are user independent^a

Implantable progestogen only hormonal contraception associated with inhibition of ovulation^b

- Intrauterine device (IUD)
- Intrauterine hormone-releasing system (IUS)
- Bilateral tubal occlusion

Vasectomized partner

A vasectomized partner is a highly effective contraception method provided that the partner is the sole male sexual partner of the woman of childbearing potential (WOCBP) and the absence of sperm has been confirmed. If not, an additional highly effective method of contraception should be used.

Sexual abstinence

Sexual abstinence is considered a highly effective method only if defined as refraining from heterosexual intercourse during the entire period of risk associated with the study intervention. The reliability of sexual abstinence needs to be evaluated in relation to the duration of the study and the preferred and usual lifestyle of the participant.

NOTES:

a Typical use failure rates may differ from those when used consistently and correctly. Use should be consistent with local regulations regarding the use of contraceptive methods for participants participating in clinical studies.

b Hormonal contraception may be susceptible to interaction with the study intervention, which may reduce the efficacy of the contraceptive method. In this case, 2 highly effective methods of contraception should be utilized during the intervention period and for at least 3 months after the last dose of study intervention

COLLECTION OF PREGNANCY INFORMATION:

Male participants with partners who become pregnant

- The Investigator will attempt to collect pregnancy information on any male participant's female partner who becomes pregnant 2 weeks before the first dose of isatuximab treatment, while the male participant is in the study, and within 5 months after the last dose of isatuximab treatment.
- After obtaining the necessary signed informed consent from the pregnant female partner directly, the Investigator will record pregnancy information on the appropriate form and submit it to the Sponsor within 24 hours of learning of the partner's pregnancy. The female partner will also be followed to determine the outcome of the pregnancy. Information on the status of the mother and child will be forwarded to the Sponsor. If applicable, the follow-up will be approximately at least 1 year after the birth. Any termination of the pregnancy will be reported regardless of fetal status (presence or absence of anomalies) or indication for the procedure.

Female participants who become pregnant

- The Investigator will collect pregnancy information on any female participant who becomes pregnant 2 weeks before the first dose of isatuximab treatment, while participating in the study, and within 5 months after the last dose of isatuximab treatment. Information will be recorded on the appropriate form and submitted to the Sponsor within 24 hours of learning of a participant's pregnancy. The participant will be followed to determine the outcome of the pregnancy. The Investigator will collect follow-up information on the participant and the neonate and the information will be forwarded to the Sponsor. If applicable, the follow-up will be approximately at least 1 year after the birth. Any termination of pregnancy will be reported, regardless of fetal status (presence or absence of anomalies) or indication for the procedure.
- Any pregnancy complication or elective termination of a pregnancy will be reported as an AE or SAE. A spontaneous abortion is always considered to be an SAE and will be reported as such. Any post-study pregnancy related SAE considered reasonably related to the study intervention by the Investigator will be reported to the Sponsor as described in [Section 8.3.4](#). While the Investigator is not obligated to actively seek this information in former study participants, he or she may learn of an SAE through spontaneous reporting.
- Any female participant who becomes pregnant while participating in the study will discontinue study intervention or be withdrawn from the study.

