1.3 SCHEDULE OF ACTIVITIES (SOA)

Procedure	Screening (up to 28 days before Day 1)	Treatment Period (12 weeks)								Site Visit FUP (26 weeks) ^a	E/D ^b	Extended FUP ^c	Notes All on-treatment procedures should be performed prior to IMP administration unless indicated otherwise				
		Cycle 1 (28 Days)				Cycle 2 (28 days)		Cycle 3 (28 days)									
		D1	D8	D15	D22	D1	D15	D1	D15								
Time Window (days)		±1	±1	±1	±1	±2	±2	±2	±2	±7	±7	±7					
Informed consent	X												Informed consent may be signed prior to D- 28				
Inclusion and exclusion criteria	X																
Demography	X												Date or year of birth (depending on local regulation), sex, ethnicity, and race (if local regulation allows)				
Medical, disease, and surgical history	X												Include start date of dialysis				
Sensitizing events	X	←=====→											Collect dates and types of relevant sensitizing events that can impact cPRA (eg, Blood transfusion)				
HLA tissue typing (collect data on already available results is acceptable)	X												For screening (can be done prior to D-28), enter the most recent results if available				
12-lead ECG	X												See Section 8.2.3				

Procedure	Screening (up to 28 days before Day 1)	Treatment Period (12 weeks)								Site Visit FUP (26 weeks) ^a	E/D ^b	Extended FUP ^c	Notes All on-treatment procedures should be performed prior to IMP administration unless indicated otherwise				
		Cycle 1 (28 Days)				Cycle 2 (28 days)		Cycle 3 (28 days)									
		D1	D8	D15	D22	D1	D15	D1	D15								
Time Window (days)		±1	±1	±1	±1	±2	±2	±2	±2	±7	±7	±7					
Echocardiography	X												Should be performed at dry weight, and/or on a non-dialysis day (see Section 8.2.4)				
Full physical examination including height (screening only) and weight	X (≤7 days prior to first IMP)	X		X		X		X		X (Weeks 1 and 9 only)	X		See Section 8.2.1				
Vital signs ^d	X	X	X	X	X	X	X	X	X	X (Weeks 1 and 9 only)	X		See Section 8.2.2)				
Pregnancy test (WOCBP)	X (≤7 days prior to first IMP)					X		X		X ^e (Week 1, and 5 months after last dose)	X ^e		Serum pregnancy test at screening; serum or urine hCG pregnancy test at other time points See Section 10.2				
HBV, HCV, HIV, CMV, EBV	X	As clinically indicated								X ^f	X ^g		See Section 10.2				
Laboratory assessments (blood chemistry, hematology)	X (≤14 days prior to first IMP)	X ^h		X		X		X		X (Weeks 1 and 9 only)	X		See Section 10.2				

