- e Pregnancy test can be performed at home for participants during the FUP or if date of test does not match with FUP visit and the site must record this in the source document. Test should be performed at the end of isatuximab treatment (ie, Week 1 of site visit FUP or E/D visit [± 7 days]), and 5 months (± 7 days) after the last dose of IMP.
- f Post-treatment tests are only applicable for HBV, CMV, and EBV, and only has to be performed at Site Visit FUP Week 9 if baseline result is positive or as clinically indicated. In case HBV vaccination will be started before first study treatment administration, anti-HBs should be monitored at approximately 1, 2, and 3 months after end of vaccination (± 7 days, or at the next blood sampling). For participants with positive anti-HBc and negative HBsAg and undetectable HBV deoxyribonucleic acid (DNA) at study entry (past resolved infection, resolving acute infection, or receiving antiviral treatment with controlled infection), close monitoring of viral reactivation (greater than 1log10 IU/mL increase in HBV DNA or reappearance of HBsAg or detection of HBV DNA in patients with resolved infection) throughout and following the end of study

treatment should be proposed (alanine aminotransferase [ALT], aspartate aminotransferase [AST], and HBV DNA at Site Visit FUP Week 9 and Week 25, or until initiation of further desensitization therapy/transplant surgery). In case of viral reactivation during study treatment (greater than 1log10 IU/mL increase in HBV DNA or reappearance of HBsAg or detection of HBV DNA in participants with resolved infection), close monitoring of ALT and AST approximately every month (may coincide with the next scheduled blood sampling \pm 7 days), up to study treatment discontinuation. HBV DNA to be done as per Investigator's and/or specialist advice.

- g Only if screening result is positive and not tested during site visit FUP.
- h Assessment not required to be repeated prior to Cycle 1 Day 1, if screening assessments were performed within 7 days prior to the first IMP infusion and met the entry criteria. Window for assessment is within 1 working day prior to IMP infusion.

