5.1 INCLUSION CRITERIA

Participants are eligible to be included in the study only if all of the following criteria apply:

Age

I 01. Participant must be 18 to 70 years of age inclusive, at the time of signing the informed consent.

Type of participant and disease characteristics

I 02. Diagnosis of CKD and active candidate on the kidney waitlist at the time of screening.

For Participants in Cohort A:

I 03. cPRA \geq 99.90% within 4 weeks of IMP initiation as per local laboratory assessment (unacceptable antigens defined as MFI \geq 2000), and stable within 6 months prior to IMP initiation based on medical history or samples, if available.

For participants in Cohort B:

I 04. cPRA 80.00% to 99.89% within 4 weeks of IMP initiation as per local laboratory assessment (unacceptable antigens defined as MFI \geq 2000), and stable within 6 months prior to IMP initiation based on medical history or samples, if available.

I 05. Participant with no living donor cleared for donation at the time of screening.

Weight

I 06. Body mass index (BMI) \leq 40 kg/m².

Sex

I 07. Male or Female

Contraceptive use by men or women should be consistent with local regulations regarding the methods of contraception for those participating in clinical studies.

a) Male participants

Male participants with female partners of childbearing potential are required to use effective contraceptive methods as detailed in Appendix 4 ([Section 10.4](#)) of this protocol starting 2 weeks before IMP administration, during treatment period, and until 5 months after last dose of isatuximab.

b) Female participants

Female participants of childbearing potential are required to use effective contraceptive methods as detailed in Appendix 4 ([Section 10.4](#)) of this protocol starting 2 weeks before IMP administration, during treatment period, and until 5 months after last dose of isatuximab. Female participants of childbearing potential must be willing or able to be tested for pregnancy (see [Section 10.4](#) for details).

Informed Consent

I 08. Capable of giving signed informed consent as described in Appendix 1 ([Section 10.1](#)) which includes compliance with the requirements and restrictions listed in the informed consent form (ICF) and in this protocol.

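### The back-up contraceptive method in Table 12 footnote b may stop 3 months after the last dose, although the protocol requires contraception for 5 months

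*Protocol*

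**What the plan says.** Inclusion criterion I 07 (Protocol Section 5.1) requires contraception for women of childbearing potential, and for men with partners of childbearing potential, from 2 weeks before the first dose and "until 5 months after last dose of isatuximab". The contraception guidance in Appendix 4 (Section 10.4) repeats the rule: "during treatment period, and until 5 months after last dose of isatuximab".

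Within Appendix 4, women of childbearing potential must "agree to use a highly effective method of contraception consistently and correctly as described in" Table 12. Two hormonal entries in that table carry marker b:

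- "Combined (estrogen and progestogen containing) hormonal contraception associated with inhibition of ovulation^b"
- "Implantable progestogen only hormonal contraception associated with inhibition of ovulation^b"

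Footnote b says that hormonal contraception may interact with the study intervention and lose efficacy, and that, where this applies, "2 highly effective methods of contraception should be utilized during the intervention period and for at least 3 months after the last dose".

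Pregnancy surveillance also uses 5 months. The pregnancy-test row of the Schedule of Activities (Section 1.3) places the post-treatment tests at "Week 1, and 5 months after last dose". Footnote e of that schedule and Appendix 2 (Section 10.2) give the same final time point. Section 8.3.5 and the pregnancy-collection part of Appendix 4 collect pregnancies up to 5 months after the last dose.

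**The concern.** The second method exists because the first may be impaired. One would expect that safeguard to last as long as contraception itself is required. In footnote b it may end 2 months sooner, and neither the protocol text nor either amendment log explains why.

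Table 12 classes both marked entries as highly effective, and the duty outside the footnote is for a single highly effective method. A woman using a combined hormonal method or a progestogen implant, for whom an interaction is suspected, could therefore stop the second method at month 3. She would then rely until month 5 on the hormonal method alone and still comply with the text. At stake is protection against pregnancy in a period when the protocol itself requires that protection.

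**Working it through.** There is no statistical quantity to reproduce. The check sets the stated durations side by side and asks what they jointly allow.

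| Provision | Where | Length after last dose |
|---|---|---|
| Contraception required | Section 5.1, I 07 | 5 months |
| Contraception required | Section 10.4, contraception guidance | 5 months |
| Last pregnancy test | Section 1.3 (test row and footnote e); Section 10.2 | 5 months (± 7 days) |
| Pregnancy information collected | Section 8.3.5; Section 10.4 | 5 months |
| Two methods where a hormonal method may be weakened | Section 10.4, Table 12 footnote b | at least 3 months |

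Size of the gap:

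- 5 − 3 = 2 months, which is 2/5 = 40% of the post-dose contraception period.
- In days, with 365.25/12 = 30.44 days per month: 3 × 30.44 ≈ day 91 and 5 × 30.44 ≈ day 152, so 152 − 91 = 61 days.

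What the rules jointly require of a woman using a marked method when an interaction is suspected:

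1. From the first dose to month 3 after the last dose: two highly effective methods (footnote b).
2. From month 3 to month 5: one highly effective method (I 07 and Appendix 4). Table 12 accepts the marked hormonal method as one.
3. After month 5: no requirement.

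Step 2 is the gap. Other parts of Appendix 4 follow the full period. Abstinence counts only if it covers the whole period of risk. Men with partners of childbearing potential who are not abstinent must use a condom plus a further method throughout the protocol-defined period, with no earlier cut-off for the second method.

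**The case against.** The strongest reply is that nothing conflicts. The 5-month rule says how long contraception is needed. Footnote b says how long a second method is added in one conditional situation, and it sets only a minimum. A site can obey every sentence. This is correct, and the point is not presented as a contradiction.

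A second reply is that the two periods need not be equal. The footnote concerns a possible interaction with the contraceptive, and no text says such an interaction would last 5 months. This is also fair: the documents do not prove that 5 months is needed. But they do not support 3 either, and the only post-dose contraception period they otherwise state is 5 months.

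Third, a method truly weakened by an interaction might no longer count as highly effective, in which case the single-method duty would itself exclude it. The documents do not settle this. Table 12 lists the method as highly effective without that qualification, so a site reading the table could accept it.

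Fourth, the trigger may never arise. The documents report no interaction between isatuximab and hormonal contraceptives, and Section 4.3 describes an antibody expected to be cleared by proteolytic catabolism. This limits the importance of the point. It does not explain why the precaution, once kept in the protocol, should end before the required period does.

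Finally, the scope is slightly uncertain. Marker b appears on two entries, while the footnote's wording refers to hormonal contraception in general, and the oral or injectable progestogen-only entry is unmarked.

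**Conclusion.** The point holds as a minor inconsistency in the safety text. For 2 of the 5 post-dose months, the minimum in footnote b lets the back-up method stop while contraception is still required. The 40% and the 61 days describe the gap between two texts and do not measure pregnancy risk.

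The conclusion rests on two readings: that the marked methods continue to count as highly effective because Table 12 lists them so, and that sites will apply the stated minimum as the rule. It matters only if an interaction is suspected in a woman using a covered method. How many women that would be cannot be derived from the documents and could be none. No endpoint, sample size or analysis changes.

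**What to change.** In Table 12 footnote b, replace the 3-month minimum with 5 months after the last dose of study intervention, so that it matches I 07 and the Appendix 4 guidance. The gap then falls from 2 months to 0. If 3 months was intended, one sentence explaining why the shorter period is enough would also settle the matter.

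The edit is one number in one footnote and can go into the next amendment. It adds no visit, test or data item. Its cost falls on the women the footnote covers: up to 2 more months of dual contraception.
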